#### 3. STUDY OBJECTIVES AND ENDPOINTS

### 3.1. Study Objectives

#### 3.1.1. Primary Objectives

- To evaluate ORR in cholangiocarcinoma (intra-hepatic [iCCA] or extra-hepatic [eCCA]) patients with tumors harboring FGFR2 gene fusions or other FGFR abnormalities
- To evaluate ORR and EPR (defined as progression-free rate at the end of Cycle 2) in patients with primary CNS tumors harboring FGFR gene fusions or FGFR1 activating mutations
- To evaluate ORR in a basket of tumor types with tumors harboring FGFR2 amplifications
- To evaluate ORR in a basket of tumor types with tumors harboring any FGFR gene fusions or activating mutations

#### 3.1.2. Secondary Objectives

- To investigate the safety of TAS-120
- To evaluate Disease Control Rate (DCR), Duration of Response (DOR) and PFS

#### 3.2. Study Endpoints

#### 3.2.1. Primary Endpoints

• Objective response rate (ORR, according to RECIST 1.1 and EPR for primary CNS tumors). Objective response rate is defined as the proportion of patients who had best overall response (BOR) of CR or PR.

#### 3.2.2. Secondary Endpoints

• Duration of response (DOR)

Duration of response is defined as the time from the first documented response (CR or PR) to the first documented objective progressive disease (PD) or death due to any cause.

• Disease control rate (DCR)

Disease control rate is defined as the proportion of patients with objective evidence of CR, PR, or SD, except that there is no requirement for a confirmation of an SD response.

• Progression-free survival (PFS)

PFS is defined as the time from the first dosing date to the date of the first documented progression or death due to any cause, whichever occurs first.

• Overall survival (OS)

OS is defined as the time between the first dosing date and the date of death.

• Safety and Tolerability of TAS-120

Safety will be analyzed through the incidence of death, adverse event, concomitant medications, physical examination, vital sign measurements, clinical laboratory results, ECG results, ECG performance status, and other safety observations at the time points indicated in the Study Schedule of Assessments (Table 1) will be monitored and recorded. The data will be summarized.

#### 4. STUDY DESCRIPTION

#### 4.1. Summary of Study Design

This is an open-label, nonrandomized, and Phase I Expansion study of TAS-120, evaluating the efficacy, safety, and antitumor activity of the RP2D of TAS-120 in patients with advanced solid tumors with FGF/FGFR-related abnormalities who have failed all standard therapies or for whom standard therapy does not exist or is not tolerated.

As of Amendment 6, the Phase 1 Dose Escalation Phase is completed and MTD/RP2D of 20 mg QD was established.

TAS-120 will be administered orally at 20 mg, QD in 21-day cycles. Approximately 185 patients will be enrolled. Patients will be assigned to one of 8 disease groups based on diagnosis, prior therapy, and FGFR aberration:

- Group 1 (Enrollment suspended as of Amendment 7): Patients with intrahepatic or extrahepatic CCA harboring FGFR2 gene fusions or rearrangements.
- Group 2: Patients with intrahepatic or extrahepatic CCA harboring FGFR2 gene fusions or rearrangements that have not received or received less than 1 cycle of prior chemotherapy (due to intolerance or patient refusal)
- Group 3 (Enrollment suspended as of Amendment 7): CCA (iCCA or eCCA) with FGFR2 gene fusions or rearrangements treated with prior FGFR inhibitors
- Group 4 (Enrollment suspended as of Amendment 7): CCA (iCCA or eCCA) with other FGFR abnormalities, i.e., gene mutations, rearrangements or amplifications
- Group 5: Patients with primary CNS tumors harboring FGFR gene fusions or FGFR1 activating mutations
- Group 6 (Enrollment suspended as of Amendment 7): Patients with advanced urothelial carcinoma harboring FGFR3 gene fusions or FGFR3 activating mutations
- Group 7: Patients with any tumor type not included in one of the prior groups, harboring FGFR2 amplification (no minimum number of copies).
- Group 8 (Enrollment suspended as of Amendment 7): Patients with any tumor type not included in one of the prior groups, harboring FGFR gene fusions or activating mutations

25 OCT 2019

### Table 1. Study Schedule for Phase 1 Expansion

NOTE: Evaluations on D1 of a cycle should be performed within 24 hours prior to dosing, unless otherwise noted. Procedures already performed during the screening period within 72 hours prior to dosing do not need to be repeated on C1D1.

The EOT visit must be performed 0-7 days after the decision is made to discontinue study treatment (for patients who discontinue at a planned study visit, that visit may be considered the EOT visit if all assessments required at EOT are performed).

	Screening Treatment Period (1 cycle = 2			21 days)	Safety Follow-up		dn-	Notes
	Period (Within 28 Days		Cycle 1	Cycles ≥2	of Tx (+0-	lays ast	al Follow Period	
	Prior to First Dose)		Day    4   8   15   (±1d   (±3d   )   )   )	Day 1 (±3d)	End of Tx ( 7 days)	30 (±3) days After Last	Survival Follow-up Period	
Written informed consent	X							
Review eligibility criteria	X	X						
Demographics/medical history	X							
Physical examination	X	X		X	X	X		
Review of pre-existing signs and symptoms	X	X						
Tumor tissue sample collection			(X)					At any time during the study; tumor tissue collection is mandatory if tissue is available.
Vital signs	X	X		X	X	X		Heart rate, blood pressure, body temperature, and respiration rate.
Height and Weight	X	X		X	X	X		Height at screening only.
Ophthalmological examination	X			(X)	X	X		At screening and 4-6 weeks after first dose; additional on-study evaluation as needed due to local requirements, physician judgment, and/or symptoms or signs of mineral deposits.
Neurological examination	X	(X)		(X)	X	X		As clinically indicated after screening, using same methods used at screening.
Neurological examination as part of RANO (Group 5)	X	(X)		(X)	X	X		For patients with primary CNS tumors, a neurological examination must be performed within 1 week of the date of the Gd-MRI performed at screening and as part of RANO response assessment.
ECOG performance status	X	X		X	X	X		

Taiho Oncology, Inc. Statistical Analysis Plan (Phase I Expansion)— Protocol: TPU-TAS-120-101

25 OCT 2019

	Screening Treatment Period (1 cycle =			21 days)		fety ow-up	dn-	Notes		
	Period (Within 28 Days	hin Cycle 1		Cycles ≥2 ± (a)	lays ast	al Follow Period				
	Prior to First Dose)	1	D 4 (±1d	8 (±3d	15 (±3d	Day 1 (±3d)	End of Tx (+0- 7 days)	30 (±3) days After Last	Survival Follow-up Period	
12-Lead Electrocardiogram	X	X	,	)	,	X	X	X		At screening and 2 hours (±15 minutes) after dosing on D1 of each cycle.
Hematology and coagulation	X	X		X	X	X	X	X		Within 24 hours prior to treatment on D1 of each cycle, any time on C1D8 and C1D15, and as clinically indicated.
Chemistry (Serum or plasma)	X	X	(X)	X	X	X	X	X		Within 24 hours prior to treatment on D1 of each cycle, any time on C1D8 and C1D15, and as clinically indicated. Additional collection for phosphorus only at C1D4.
Urinalysis (Urine dipstick)	X	X				X	X	X		
Pregnancy test	X	X				X	X	X		Serum pregnancy test required for WOCBP at screening and end of treatment; serum or urine pregnancy test required at all other timepoints.
Blood PK Sampling (Required)						X				Blood samples (1 mL) collected C2D1 pre-dose and at 1h and 3h (±30 min) post-dose. Additional samples collected pre-dose on C3D1 and C4D1.
Blood PK Sampling (Optional)		Blood samples (minimum 1 mL) any day if needed, prior to dose a 4, 6, and 24 hours post-dose.						See also protocol Section 10.13.1.		
Blood and CSF PK Sampling (Blood, CSF; Optional) (Group 5 only)						(X)				Blood and CSF samples (minimum 1 mL of whole blood and CSF each) collected 2-4 hours after dose on C2D1. See also protocol Section 10.1.1.
ctDNA blood samples	X						(X)			Minimum of 20 mL whole blood at screening (mandatory) and EOT (optional).

Taiho Oncology, Inc. Statistical Analysis Plan (Phase I Expansion)— Protocol: TPU-TAS-120-101

25 OCT 2019

	Screening	Treatment Period (1 cycle = 21 days)			21 days)	Safety Follow-up		dn-	Notes	
	Period (Within 28 Days	Cycle 1		Cycles ≥2	-0+);	lays ast	al Follow Period			
	Prior to First Dose)	1	D 4 (±1d )	ay   8 (±3d   )	15 (±3d	Day 1 (±3d)	End of Tx (	30 (±3) days After Last	Survival Follow-up Period	
CCI										
Prior & concomitant medications, AE assessments	X						• X	X		Collect from the time informed consent (ICF) is signed through 30 days after administration of the last dose of TAS-120.
Tumor assessments / scans	X					X	X		(X)	Perform the same tumor assessments/scans obtained at screening at the end of every 2 cycles (up to +2 weeks) up to Cycle 4. Thereafter tumor assessments may be performed every 3 cycles (± 7 days), or as clinically indicated, until radiologic disease progression or initiation of new anticancer therapy (whichever occurs first).  At EOT, tumor assessment must be performed if the prior scan was performed ≥9 weeks prior to discontinuation of treatment if the patient discontinued for reasons other than radiologic disease progression. See also protocol Section 10.17.  After EOT, patients who discontinued for reasons other than radiologic disease progression should continue to receive tumor assessments every 3 cycles (± 7 days), or as clinically indicated, until radiologic disease progression or initiation of new anticancer therapy (whichever occurs first).

Taiho Oncology, Inc. Statistical Analysis Plan (Phase I Expansion)— Protocol: TPU-TAS-120-101

25 OCT 2019

	Screening	Treatment Period (1 cycle = 2	Safety Follow-up	dn-	Notes	
	Period (Within 28 Davs	Cycle 1	Cycles ≥2	(+0- s) lays ast	al Follow Period	
	Prior to First	Day   4   8   15	Day	of Ty 7 days (±3) c fter L	vival ] Per	
	Dose)	1 (±1d (±3d (±3d )	1 (±3d)	End 30 Ai	Sur	
Survival status					X	After discontinuation of treatment, survival follow-up in a given group should occur every 3 months (±2 weeks) for up to 12 months after last patient enrolled in that group.
TAS-120 Dosing					Patients are required to fast for at least 2 hours before and 1 hour after each administration of TAS-120; patients are permitted to drink water during this period. TAS-120 should be administered in the morning or evening, at the same time (if possible) each day. See protocol Section 9.1.1	

#### 4.2. Treatment Assignment and Blinding/Unblinding

After the patient's initial eligibility is established and informed consent has been obtained, the 20 mg QD of TAS-120 will be administered orally in patients with tumors harboring specific FGF/FGFR aberration. The treatment of TAS-120 will be continued with 21-day treatment cycle until at least one of the criteria for study discontinuation criteria is met.

[figure not shown]
This is an open label study. The blinding/unblinding is not applicable in this study.

Primary endpoints for CCA and CNS patients, ORR will be based on the independent review of images by the Core Imaging Laboratory according to the RECIST 1.1. For the other tumor types, ORR will be based on investigators assessment.

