Please note: for patients who discontinued treatment for reasons other than disease progression, tumor assessments should be continued until radiologic disease progression or initiation of new anticancer therapy (whichever occurs first).

Solid Tumors

Measurements of solid tumors will be performed throughout study treatment using Response Evaluation Criteria in Solid Tumors (RECIST) guidelines (version 1.1, 2009). Radiographic tumor assessments (computed tomography [CT] scan with contrast will be performed at baseline and at the end of every 2 cycles (up to + 2 weeks) up to Cycle 4 (or as clinically indicated). Following Cycle 4, CT scans will be performed after every 3 cycles (\pm 7 days) or as clinically indicated, and at study completion.

Brain Tumors

Patients with brain tumors will be assessed using Response Assessment in Neuro-Oncology (RANO) criteria (2010). Patients with brain tumors will be evaluated for response by contrast magnetic resonance imaging (MRI) (gadolinium-based magnetic resonance imaging [Gd-MRI]). All MRIs should be performed when the patient is on a stable dose of steroids. Gd-MRI will be performed at baseline and at the end of every 2 cycles (up to + 2 weeks) up to Cycle 4 (or as clinically indicated). Following Cycle 4, Gd-MRI scans will be performed after every 3 cycles (\pm 7 days) or as clinically indicated, and at study completion.

Neurological examination for patients with brain tumors must always be performed within one week of the date of the Gd-MRI as part of the response assessment.

Endpoints

Phase 1 Expansion: the primary endpoint is ORR in each treatment group (and EPR for primary CNS tumors) and the secondary endpoints of DOR, DCR, PFS, and OS in each treatment group.

Phase 2: the primary endpoint is ORR and the secondary endpoints of DOR, DCR, PFS, PROs and OS.

Primary endpoints will be based on the independent review of images by the Core Imaging Laboratory. In addition, for the Phase 2 part of the study, sensitivity analyses for some key efficacy endpoints (e.g., ORR, and PFS) will be performed based on investigators or local radiologist assessments.

Statistical Methods:

Analysis Populations

The *Safety Population* will include all patients who received at least 1 dose of TAS-120. This population will be the primary population for safety evaluation.

The *DLT Evaluable Population* was defined for Phase 1 Dose Escalation only; Phase 1 Dose Escalation has been completed as of Amendment 6.

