9.17.2. Tumor Assessment for Brain Tumors

Patients will be evaluated for response by Gd-MRI. All Gd-MRIs (standard brain tumor MRI including both precontrast and postcontrast images using a Gadolinium (Gd) chelate as the contrast agent) should be performed when the patient is on a stable dose of steroids for at least 7 days. Gd-MRI will be performed at the following time points:

- Screening within 28 days prior to Day 1 of Cycle 1. Gd-MRI scans obtained prior to the signed ICF may be used as the screening scan if they were obtained within 28 days of the first dose of TAS-120.
- At the end of every 2 cycles (up to +2 weeks), up to Cycle 4, until documented progression (including after end of treatment if the patient discontinues for reasons other than radiologic disease progression).
- Following Cycle 4, at least after every 3 cycles (\pm 7 days) or as clinically indicated.
- At end of treatment (EOT), a Gd-MRI scan must be performed if the prior scan was performed \geq 9 weeks prior to discontinuation of TAS-120 treatment if the patient discontinued for reasons other than radiologic disease progression.

If a patient has a response, response confirmation should be obtained through tumor assessments/scans 4 to 6 weeks after the first documentation of response. Patients must then return to their original schedule of assessments.

Neurological examination for patients with brain tumors must always be performed within one week of the date of the Gd-MRI as part of the response assessment. Response will be based on RANO criteria.

All patients' files and radiological assessments must be available for source verification and may be submitted for extramural review for final assessment of antitumor activity. Results of any unscheduled evaluations should be recorded in the patient's source documents.

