12.2.2. Efficacy Analysis

Tumor assessments will be performed as per [Section 9.17](#), Tumor Assessments/Scans. For the Phase 1 Expansion, the primary endpoint is ORR (and EPR for primary CNS tumors), and secondary endpoints are DCR, DOR, PFS, OS.

For Phase 2, the primary endpoint is ORR and the secondary endpoints are DOR, DCR, PFS, PROs and OS (response evaluations based on independent review of images by the Core Imaging Laboratory). In addition, sensitivity analyses for some key efficacy endpoints (notably ORR and PFS) will be performed based on assessments by the investigator or local radiologist.

Response assessments will be made based on RECIST guidelines (version 1.1, 2009) for solid tumors (see [Section 10.1](#), Efficacy Assessment for Solid Tumors) or RANO for brain tumors (see [Section 10.2](#)).

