#### 6. STATISTICAL ANALYSIS

#### **6.1.** General Methods

All relevant data will be presented in patient level data listings.

All categorical (binary and ordinal) data will be summarized by tumor type groups using frequency counts and percentages of patients. Percentage will be calculated based on groups in the study population as the denominator. The continuous variables will be summarized using number of non-missing observation (n), mean, standard deviation (SD), median, minimum and maximum unless otherwise specified. The number of events and censorings will be reported for time-to-event analysis. All estimations will include a point estimate and the corresponding 95% confidence interval.

Summary tables will be presented by the disease type. Data listings will be presented with the groups and patient ID. The tables by sub-groups such as: age groups, gender, races, ECOG categories, and will be also summarized.

Analysis Cohort based on disease type (disease group 1 through group 8) are assigned as follows. Unless otherwise specified, by-cohort analysis will be included in tables and figures.

- Cohort 1: Patients with Cholangiocarcinoma (CCA). It combines disease group 1 to 4
- Cohort 2: Patients with primary CNS tumor. It's the patients from disease group 5
- Cohort 3: Patients with advanced urothelial carcinoma. It's the patients from disease group 6
- Cohort 4: Patients with breast cancer or gastric cancer. It's the patients from disease group 7
- Cohort 5: Patients with the tumor types in disease group 8, harboring FGFR gene fusions or activating mutations
- Cohort 6: Patients not included in cohort 1 to cohort 5

For concomitant medications and adverse events, the cycles are determined based on their start/onset dates. For other collected data, the cycles are determined based on their visit dates. When there are multiple laboratory records for a scheduled visit, the one closest to the target date (relative to the Day 1 in that cycle) will be used for analysis. If there are two or more records with the same time period to the target date, the later one will be used for analysis.

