#### 6.4.3. Other Efficacy Analyses

By-patient listing to include FGFR gene status, first dose date, duration of treatment, best overall response, duration of response, and cancer sub-type will be presented for each cohort.

For cohort 2 patients, response to therapy follows the RANO (Response Assessment in Neuro-Oncology) criteria. The criteria are shown in Table 8 below:

Criterion	Complete Response	Partial Response	Stable Disease	Progressive Disease
T1 enhancing disease	None	≥ 50% ↓	< 50% ↓ but <25% ↑	≥ 25% ↑ª
T2/FLAIR	Stable or ↓	Stable or ↓	Stable or ↓	↑a
New lesion	None	None	None	Present a
Corticosteroids	None	Stable or ↓	Stable or ↓	NA b
Clinical status	Stable or ↑	Stable or ↑	Stable or ↑	↓a
Requirement for response	All	All	All	Anya

Table 8. Summary of RANO Response Criteria

Abbreviations: NA=not applicable, RANO = Response Assessment in Neuro-Oncology, T1 = T1 relaxation, T2/FLAIR = T2-weighted fluid-attenuated inversion recovery.

The response results with RANO response criteria will be compared with the response results with RECIST 1.1. The best responses with the two criteria will be used and displayed in the table output. The patient level listing will be provided.

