## 7. CHANGES IN PLANNED ANALYSIS

The following table summarizes substantive changes made to the SAP in the current Amendment 1;

Section	Description of Change	Brief Rationale
Section 4.1	Text was amended as follows:	In order to be consistent with the
Summary of Study Design	Group 1 (Enrollment suspended as of Amendment 7): Patients with intrahepatic or extrahepatic CCA harboring FGFR2 gene fusions or rearrangements .  Group 2: Patients with intrahepatic or	protocol.
	extrahepatic CCA harboring FGFR2 gene fusions or rearrangements that have not received or received less than 1 cycle of prior chemotherapy (due to intolerance or patient refusal)	
	Group 3 (Enrollment suspended as of Amendment 7): CCA (iCCA or eCCA) with FGFR2 gene fusions or rearrangements treated with prior FGFR inhibitors	
Section 5.4	The following text was amended as	In order to be consistent with
Timing of Analysis	follows:	patients' follow-up time.
	The final analysis will be performed when at least 90% of all treated patients had approximately 4 months of follow-up.	

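### The Phase 1 Expansion SAP scores the primary ORR of the primary CNS group by RECIST 1.1 in section 4.2, while the protocol specifies RANO and SAP 6.4.3 does not say which criterion is primary

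*SAP*

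**What the plan says.** **Phase 1 Expansion SAP.** Section 4.2 states that "for CCA and CNS patients, ORR will be based on the independent review of images by the Core Imaging Laboratory according to the RECIST 1.1". Section 3.2.1 puts RECIST 1.1 beside ORR, adds EPR for the CNS tumours and does not mention RANO. Section 6.1 defines "Cohort 2: Patients with primary CNS tumor" and equates that cohort with disease group 5. Section 6.4.1, the primary analysis, refers to solid tumour patients and gives no criterion for the CNS group. Section 6.4.3, under other efficacy analyses, says: "For cohort 2 patients, response to therapy follows the RANO (Response Assessment in Neuro-Oncology) criteria". It continues: "The response results with RANO response criteria will be compared with the response results with RECIST 1.1". Best responses by both criteria are to be displayed.

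**Protocol.** Section 9.17.2, on brain tumours, says: "Response will be based on RANO criteria". Section 12.2.2 assigns RECIST to solid tumours "or RANO for brain tumors". The Synopsis also gives RANO for brain tumours, inclusion criterion 4 in section 7.2.1 uses RANO to define measurable disease in them, and section 10.2.3 with Table 15 sets out the RANO categories.

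**Who reads the scans.** The protocol Synopsis, protocol 10.1 and SAP 4.2 base the primary endpoint on independent review. Protocol 12.2.2.1 gives local assessment for the Expansion part, with images kept for optional central review. Protocol 9.17.1 says only that brain tumour scans may go to the core laboratory.

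**The concern.** The criterion decides who counts as a responder in a primary endpoint of Group 5. It also decides who has progressed, and so affects the group's other primary endpoint, the progression-free rate at the end of Cycle 2. A programmer working from SAP 4.2 would apply RECIST 1.1; one working from the protocol would apply RANO. SAP 6.4.3 will have both results on the page and does not say which one answers the primary objective. In an open-label study, that leaves room to choose the criterion after both results have been seen.

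**Working it through.** **1. The passages side by side (Group 5 response criterion)**

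| Place | Criterion | Named as primary? |
|---|---|---|
| Expansion SAP 3.2.1 | RECIST 1.1 beside ORR; no mention of RANO | Yes, but the wording is unclear for CNS |
| Expansion SAP 4.2 | RECIST 1.1, core laboratory | Yes |
| Expansion SAP 6.4.1 | None stated for CNS | – |
| Expansion SAP 6.4.3 | RANO, then both displayed | No |
| Protocol Synopsis, 9.17.2, 10.2.3, 12.2.2 | RANO | It is the only criterion given for brain tumours |

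The firm conflict is between SAP 4.2 and the protocol. SAP 6.4.3 points to RANO but does not settle the matter.

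**2. Do the size thresholds differ?** Inputs are from protocol 10.1.3.1 (RECIST: PR is a 30% fall and PD a 20% rise in the sum of diameters) and 10.2.3 (RANO: PR is a 50% fall and PD a 25% rise in the sum of products of perpendicular diameters). Assume that a lesion changes uniformly, so area scales as diameter squared. The same geometry reproduces the protocol's own conversion in 10.1.3.1: 1.20³ − 1 = 0.728, stated there as 73% in volume.

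- PR: RECIST 1 − 0.70² = 0.51, a 51% fall in area, against 50% for RANO. In diameter, RANO is 1 − √0.50 = 0.293, against 30%. The cut-offs nearly coincide.
- PD: RECIST 1.20² − 1 = 0.44, a 44% rise in area, against 25% for RANO. In diameter, RANO is √1.25 − 1 = 0.118, against 20%. RECIST also requires an absolute rise of 5 mm.

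Growth of 25% up to 44% in area is therefore progression by RANO and not by RECIST on size alone.

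**3. Conditions other than size.** Under protocol 10.2.3, RANO PR also needs a steroid dose no higher than at the baseline scan, stable or improved clinical status, and stable or improved non-enhancing disease. A patient whose lesions shrink past both size cut-offs on a raised steroid dose is a PR by RECIST and not by RANO. The reverse can happen when shrinkage is not uniform: if the perpendicular diameter halves and the longest is unchanged, the product falls by 1 − 1 × 0.5 = 50% while the longest diameter falls by 0%. The net direction is therefore not known.

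**4. Size of the effect on ORR.** Each reclassified patient moves ORR by 100/n points. The Group 5 n is redacted. For assumed n of 10, 20 or 40 the shift is 10.0, 5.0 or 2.5 points per patient. The number reclassified cannot be derived from the documents.

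**5. The Cycle 2 endpoint.** Both documents define EPR as the progression-free rate at the end of Cycle 2 (protocol 6.2 and 12.2.2.4; Expansion SAP 3.1.1), but their abbreviation lists call it the early progression rate, which is the complement. SAP 6.1 has a general Kaplan-Meier rule for rates at fixed times that can cover it. End of Cycle 2 is 2 × 21 = day 42, and the scan may be up to 2 weeks late, that is to day 56, so the reading day should be written down.

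**The case against.** The best defence is that SAP 3.2.1, 4.2 and 6.4.3 can be read together as RECIST 1.1 primary with RANO as an added display. The RANO data are also being collected, since the SAP schedule requires the neurological examination for the RANO assessment, and both results will be shown. Group 5 is one Expansion cohort, and the Phase 2 primary endpoint is untouched. Part of this stands: 6.4.3 ranks neither criterion, so it would go too far to say that it already makes RANO primary and RECIST supportive. But the defence leaves the SAP at odds with the protocol on a primary endpoint.

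Three stronger readings are tempting, and the documents do not support them.

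- *An undeclared switch.* A reader might infer one because SAP section 7 lists no move to RECIST. That section opens: "The following table summarizes substantive changes made to the SAP in the current Amendment 1". It logs revisions to the SAP, not departures from the protocol, so its silence proves nothing.
- *PR made impossible.* Protocol 10.1.2 always makes the primary lesion non-target, and Table 14 for non-target-only disease has no PR row. A reader might conclude that a lone brain tumour could never reach PR under RECIST. Those rules sit in the solid-tumour section 10.1. Brain tumours have their own section 10.2, no text applies the 10.1.2 rule to Group 5, and the imaging charter is not available.
- *A faulty EPR analysis.* The definition is consistent, SAP 6.1 offers a usable rule, and the Group 5 design and boundaries are redacted. A curve read exactly on day 42 could differ widely from one read when the scan window closes, but no visible text chooses day 42.

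**Conclusion.** The point holds. As written, Expansion SAP 4.2 would score the Group 5 primary ORR by a criterion that the protocol does not use for brain tumours, and nothing visible in the SAP names the primary criterion consistently with the protocol. It should be fixed before the Expansion analysis.

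The criteria are close on the size threshold for PR. They differ on the added RANO response conditions and, under the uniform-growth assumption, on the size threshold for PD. The size and direction of the effect on ORR are not known; only the shift per reclassified patient can be given, for an assumed n. The EPR label is a secondary, editorial matter, and no estimator or boundary error is shown. The conflict over independent or local reading is a separate inconsistency bearing on the same endpoint.

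**What to change.** 1. In Expansion SAP 3.2.1, 4.2 and 6.4.1, name RANO as the primary criterion for Group 5 ORR and for progression in the Cycle 2 endpoint. In 6.4.3, label RECIST 1.1 as supportive. If RECIST 1.1 is truly intended as primary, declare the departure from the protocol and justify it.
2. State one reader for the Group 5 primary endpoint, and align the protocol Synopsis, 9.17.1, 10.1 and 12.2.2.1 with SAP 4.2.
3. Replace the label EPR with progression-free rate at the end of Cycle 2 and keep the definition. Confirm that its direction, the SAP 6.1 fixed-time rule and the reading day match the redacted Group 5 design, and state how patients without an end-of-Cycle-2 scan count.
4. Editorial: protocol 10.1 and 12.2.2.4 still tie EPR to glioblastoma or grade III glioma; align them with the current Group 5 population.

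The cost is wording and table labels, since 6.4.3 already plans output by both criteria. A central RANO read adds cost only if it is chosen as primary and does not already exist.
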